5.6 Independent Review

All statistical analyses for primary reporting of trial results will be independently verified through dual programming and/or code review. Two statisticians will each program all datasets and trial results analyses for the DSMB reports and the primary manuscript and the results will be compared.

6 INTERIM ANALYSES

6.1 Frequency of and Timepoints for Interim Analysis

There are two classes of interim analyses: a set of inferential statistical analyses for a formal interim stopping rule; and largely descriptive summaries focusing on data and safety monitoring used in reports prepared for the DSMB. The statistical testing underlying the formal stopping rule will be conducted when every new batch of five additional participants for whom has the site reported the primary safety outcome occurred has undergone the adjudication process. Details of this testing are provided in Section 6.4.

A DSMB report with safety and data completion metrics will be prepared and distributed to the DSMB for every DSMB meeting during enrollment. Scheduled DSMB meetings are intended to be held twice during the study: approximately 8 weeks after the tenth participant randomization, and approximately 8 weeks after the 25th participant randomization.

6.2 Stopping Rules for Interim Efficacy Analysis

This study is not intended to provide definitive efficacy assessments, even at study conclusion. As such, early stopping for efficacy is not a consideration.

6.3 Futility Monitoring in the Interim Analysis

Because the study is not intended to provide definitive efficacy assessments, early stopping for the futility of demonstrating efficacy is also not a consideration.

6.4 Early Trial Termination for Safety

Tests of the primary safety outcome will be conducted from the SAFETY population (see Section 4.2.7). Per the DSMB guidance, we increased the planned frequency of comparing the primary safety outcome between treatment arms for the purpose of applying early trial termination criteria. Instead of one interim analysis after 25 enrollments, testing for a difference between treatment arms in the proportion of enrolled patients experiencing the primary safety outcome, a group sequential approach will be taken.

After the adjudication of every 5 new patients who were reported by the site to have had the primary safety outcome, we will conduct a two-sided Fisher's exact test using an alpha threshold of 0.0333.¹ Each test will include those with a known outcome at the time the

¹This p-value threshold was chosen so that, accounting for the varying number of interim tests that may be conducted, the overall type I error rate is close to 0.05. The SAP's Appendix contains a detailed motivation for the 0.0333 threshold at each interim look.

Interim stopping rule example. After every 5 patients with safety outcome, conduct Fisher's exact test at alpha=0.0333. Example below assumes at each test, 50% of patients had safety outcome and enrollment was balanced between Arms A and B

adjudication process is completed (even if for a participant enrolled after the fifth new reported event), with participants for whom the outcome has not yet been determined being excluded until the outcome has been determined. We will test the null hypothesis that the two treatment strategies have the same expected proportion of patients who will experience the primary safety outcome. If a test is significant, we will stop the trial for safety reasons.

Many factors may influence exactly what the stopping rule thresholds are in the trial, such as primary safety outcomes that are overruled by the adjudication panel (expected to be uncommon), the underlying event rate, and the balance of randomization to treatment arms throughout the trial.

Figure 6.4 is an illustrative example of how the rule translates to go/no-go thresholds under one particular set of assumptions:

- At every interim look, there have been equal numbers randomized to each treatment.
- At every interim look, half of the total number of enrolled patients have experienced the primary safety outcome (though the numbers can differ by arm)

Note that the primary safety outcome will also be tested for a difference in arms after all participants have been enrolled, again using the 0.0333 threshold to be declared statistically significant, unless a previous test was already significant at this threshold. However, this is not considered an interim analysis because it is after all participants were enrolled.

6.5 Subgroups in the Interim Analysis

Interim DSMB reports will provide information overall (and by treatment group for the closed session). In addition, select summaries (e.g., enrollment rates) may be provided by site to possibly inform training or monitoring efforts.

6.6 Blinding in the Interim Analysis

Interim DSMB reports will only show information by treatment arm in the closed session report. The closed session reports will be made available to unblinded DCC statisticians and DSMB members but not to clinical staff or study investigators.

7 PLANNED ANALYSES

7.1 Description of Participant Characteristics

Summaries of enrolled participants will be provided for baseline characteristics such as, but not necessarily limited to, the following:

- age
- sex
- race/ethnicity
- number of platelet transfusions between cannulation and consenting process and if those transfusions were prophylactic or therapeutic (i.e., to treat active bleeding)
- bleeding between cannulation and enrollment

Summaries of nominal variables will be comprised of frequencies and percentages. Summaries of (quasi-)continuous variables will be comprised of means and standard deviations, and/or medians, first quartiles, and third quartiles, as deemed appropriate. Summaries of ordinal variables may use frequencies with percentages, means with standard deviations, or medians with first and third quartiles, as deemed most suitable.

7.2 Primary Outcome Analysis

For the pilot study, the analysis of the primary outcome measure will be assessing the pretransfusion platelet count to describe the separation between the two platelet transfusion strategies, while accounting for intra-subject correlation. For each arm, we will estimate the mean pre-transfusion platelet count from randomization to the permanent discontinuation of the treatment strategy. This primary outcome will be measured for each transfusion and represent the latest available collected platelet count that is before the transfusion began and not before a prior transfusion. In the event that there was no preceding platelet count since a previous transfusion, the outcome for that transfusion will be regarded as missing. Participants who do not have a nonmissing value for this outcome (e.g., they had no transfusions) will not be included in the analysis of the primary outcome. Thus, the primary outcome uses all transfusions with non-missing pre-transfusion platelet counts during the period between randomization and the final termination of the transfusion strategy being in effect (whether or not during a temporary suspension) from all ITT patients with at least one such transfusion having a non-missing pre-transfusion platelet count.

7.2.1 Primary Analysis for Aim 1

The first objective is based on the primary outcome of platelet counts before transfusions. Because we anticipate intra-subject correlation when there are multiple transfusions for a participant, we will fit a linear model to pre-transfusion platelet counts with a fixed effect for assigned treatment (Higher threshold, with tmt=1, vs Lower threshold, with tmt=0), such that the outcome's expected value is represented by $\beta_0 + \beta_{tmt}$ for the higher threshold and β_0 for the lower threshold. We will account for repeated measures by considering three covariance structures: compound symmetry (CS), continuous analog of autoregressive order 1, also known as CAR(1), and a hybrid of CS and CAR(1) achieved by including random subject effects and CAR(1) correlations in the within-subject errors. We will use restricted maximum likelihood (REML) for model estimation and use the model with the lowest Akaike Information Criterion (AIC) to select the best covariance structure. Once the covariance structure is determined, the Kenward-Roger calculation for denominator degrees of freedom (df) will be applied in the F-test (equivalently, for the df in the t-test) of the treatment strategy's model coefficient. The one-sided p-value of the null hypothesis $\beta_{tmt} = 0$ vs $\beta_{tmt} > 0$ will be considered statistically significant if and only if this p-value < 0.025. In addition, a two-sided 95% confidence interval for β_{tmt} will be reported. Likewise, estimated means for the lower threshold and the higher threshold arms will be reported as $\hat{\beta}_0$ and $\hat{\beta}_0 + \hat{\beta}_{tmt}$ respectively.

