H. Temporary suspension of Individual Patients

The protocol will allow for temporary suspensions, i.e., transfusion at a higher platelet count threshold than allowed for the randomization arm, if the clinical situation warrants immediate transfusion for certain conditions including: 1) chest-tube insertion; 2) surgical intervention while on ECMO (such as tracheostomy or repair of congenital diaphragmatic hernia); 3) during ECMO circuit change; or 4) in preparation for decannulation. In addition, while patients will be monitored for severe bleeding and/or severe clotting events during this time, they will not have the transfusion strategy permanently discontinued if they develop such an event during the temporary suspension, provided that the severe bleeding/clotting has resolved within the 24 hours of the temporary suspension. If a patient continues to have severe bleeding or severe clotting past the 24 hours of the temporary suspension, the intervention is stopped.

Adherence to the trial protocol must be resumed as soon as possible once these events are controlled or completed. Data monitoring and collection will be unchanged during suspension (including pre-transfusion platelet counts and platelet transfusion volumes), but data on length and justification of suspension will also be collected. Suspensions less than 24 hours will not be considered a breach of adherence to the protocol. After 24 hours of temporary suspension, the patient will have all assigned treatment strategy implications lifted (i.e., no restrictions on the range at which any subsequent platelet transfusions may occur) but will continue to be followed for ascertainment of safety and study outcomes. Temporary suspensions will only necessitate exclusion from analyses for one of the secondary endpoints (#6: proportion of compliant platelet transfusion actions), as explicitly noted in Section 9.B. The safety outcomes will still be followed but will be analyzed as a sub-group (e.g., severe bleeding during temporary suspensions).

9. Outcomes

The objective for the **pilot study** will be to assess the **feasibility** of the full RCT.

A. Primary Outcome

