The primary objective is to assess the separation between the higher and lower platelet threshold arms. Indeed, for a transfusion trial to be successful, there has to be a clinically meaningful separation between the transfusion strategies, to be able to imply causality for the outcome. Since the higher platelet threshold is $<90 \times 10^{9}$ /L and the lower platelet threshold is $<50 \times 10^{9}$ /L, we expect the **separation of the pre-transfusion platelet count (primary outcome) to be at least 30 x10⁹/L**. To assess the separation between both arms, we will collect the pre-transfusion platelet count before each transfusion event.

In addition, we will collect the total daily platelet transfusion dose for a patient while the patient is on ECMO. The average daily dose (in ml/kg/day) will be computed by the research team, by dividing the total platelet transfusion volume by the patient's weight at admission and the number of days on ECMO.

These outcomes will be measured outside of temporary suspensions; that is, transfusions occurring during a temporary suspension are ignored from these analyses.

The primary *safety* outcome, which is assessed in conjunction with the early trial stopping rule, is occurrence of any of the following from the time of randomization (enrollment) to 24 hours after the transfusion strategy threshold was permanently discontinued: progression from no bleeding or minimal bleeding to severe bleeding, according to the BASIC definition (34); severe thrombotic event, according to the NHLBI Hemostasis Clinical Trial Outcomes Working Group (need for circuit change, need for thrombectomy, ischemic stroke, or distal thromboembolism, as diagnosed clinically) (48); death (i.e., all-cause mortality). The primary safety outcome ignores severe bleeding/severe clotting that begins during a period of temporary suspension, but does not ignore deaths that occur during a period of temporary suspension.

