- Proportion of compliant platelet transfusion actions (examples of noncompliance are transfusion given at or above threshold or without any platelet count in the previous 12 hours, excluding transfusions given during a temporary suspension, or transfusion not given within 12 hours of a platelet count below threshold) > 90% (see Appendix F for details);
- Proportion of patients with one or more temporary suspensions not due to preparation for decannulation < 10%;

- 8. Proportion of patients who withdraw from the study and/or are lost to follow-up (i.e., withdraw and/or are missing 90-day mortality assessment) < 6%;
- Proportion of patients with non-platelet transfusion protocol violations (violation of sitespecific management protocol for any aspect besides platelet transfusion threshold compliance) < 5%;
- 10. First instance of progression to severe bleeding or thrombotic outcomes can be adjudicated in > 90% of the patients for whom such an outcome was reported by the site.

Similar to pre-transfusion platelet counts, overall platelet transfusion doses, and progression to severe bleeding and/or clotting, feasibility outcomes 1, 6, and 9, are to be analyzed outside of temporary suspensions.

C. Tertiary Outcomes

Our tertiary outcome is to demonstrate the ability for an adjudication committee to determine the severity of bleeding and/or thrombotic outcomes.

This is similar to the primary safety outcome, except that it does not include mortality in the definition. That is, progression to severe bleeding or a severe clotting event must occur, whether or not there is an all-cause death. We will demonstrate that the recorded data is sufficient for the adjudication of severe bleeding, severe thrombus or both in 90% of enrolled subjects with this outcome reported by the site.

Justification of BASIC and NHLBI definitions of bleeding and thrombosis:

We believe that the BASIC (34) (Table 1) and NHLBI definitions (48) of bleeding and thrombosis provide the most relevant descriptions as they relate to children supported by ECMO. Importantly, central nervous system involvement, a frequent site of bleeding on ECMO, may be captured by a

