- With n=30 participants, either ≤4 (≤26.7%) or ≥11 (≥73%) out of 15 in the lower threshold arm
- With n=40 participants, either ≤6 (≤30%) or ≥14 (≥70%) out of 20 in the lower threshold arm
- With n=50 participants, either ≤8 (≤32%) or ≥17 (≥68%) out of 25 in the lower threshold arm

D. Limitations with Strategies to Overcome

- Sites may not be able to maintain clinical equipoise throughout the study period, as the study is not blinded. To compensate for this, prior to the study initiation, we will present the study protocol to leaders in the ECMO team at each site, including general surgeons, cardiothoracic surgeons, anesthesiologists, neonatologists, and pediatric intensivists to ensure compliance. We will review compliance for each site at monthly meetings and at the interim analysis and provide further education at each site as needed. Moreover, we will highlight the fact that the full ECSTATIC study will be a non-inferiority RCT, which underlines that we expect to find no statistically significant difference in the outcomes of the patients who will participate in the large study.
- The proportion of platelets transfused during temporary suspensions may dilute the separation between platelet exposure between the two arms. For this reason, we have limited the number of reasons for temporary suspensions. We will also analyze the impact of suspensions on the platelet count separation.
- Different methods can be used to obtain platelet products: 13% of platelet transfusions given to ECMO patients are whole blood derived - either by platelet-rich plasma (USA and UK) or the buffy-coat method (Europe and Canada), and 87% are obtained by apheresis (singledonor) (13). The volume of a whole blood derived platelet unit is about 50 mL while that of an apheresis platelet unit ranges from 200 to 300 mL. We will not be able to control the methods of processing platelets at each site. However, processing details of each platelet transfusion will be recorded. At least five of the ten participating sites will be reporting the number of platelets per mL of transfusate received so that we can describe the dose of platelets

transfused and consider controlling for this in the larger trial. Though it is not feasible in the pilot due to cost, we will consider assaying the transfusates themselves in the larger trial to determine the actual platelet count transfused.

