5.5 Derived and Computed Variables

Derived variables needed for analysis will be defined in a corresponding data dictionary. Most variables of particular importance were already defined. Select variables of particular importance are defined in the remainder of this subsection.

Additional outcomes: transfusion volumes in mL/kg/run and mL/kg/day. These are the total platelet transfusion doses while on ECMO in mL/kg/run, and the transfusion dose in mL/kg/hr (or its redundant value, in mL/kg/day, obtained by multiplying the dose in mL/kg/hr by 24). When determining the total mL/kg of the platelet transfusions, all doses given from randomization until the permanent discontinuation of the transfusion strategy will be counted, whether or not the dose was transfused during a temporary suspension of the assigned strategy. The total transfusion dose measured in mL/kg/run is simply the mL/kg during this acute follow-up phase, whereas the dose in mL/kg/day is the total dose in mL/kg divided by the number of hours from randomization until permanent strategy discontinuation.

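### The protocol (9.A, 9.B) excludes transfusions given during temporary suspensions from the primary outcome and the dose; the SAP (7.2, 5.5) includes them, so the only powered test has two definitions

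*Combined protocol and SAP*

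**What the plan says.** **Exclusion.** Protocol 9.A defines the primary outcome (the pre-transfusion platelet count) and the average daily platelet dose, then states: "These outcomes will be measured outside of temporary suspensions; that is, transfusions occurring during a temporary suspension are ignored from these analyses". Protocol 9.B repeats the rule. Its closing sentence begins "Similar to pre-transfusion platelet counts, overall platelet transfusion doses" and goes on to say that "feasibility outcomes 1, 6, and 9, are to be analyzed outside of temporary suspensions".

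**Inclusion.** SAP 7.2 defines the analysis set as all transfusions with a non-missing pre-transfusion count between randomization and the "final termination of the transfusion strategy being in effect (whether or not during a temporary suspension) from all ITT patients" who have at least one such transfusion. SAP 5.5 says that all doses up to permanent discontinuation "will be counted, whether or not the dose was transfused during a temporary suspension of the assigned strategy". SE1 takes its estimate from the SAP 7.2.1 model, so it inherits inclusion. SAP SE9 contains no exclusion for suspensions.

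**A third statement.** Protocol 8.H says that suspensions require exclusion only for "one of the secondary endpoints (#6: proportion of compliant platelet transfusion actions), as explicitly noted in Section 9.B". Section 9.B in fact lists outcomes 1, 6 and 9.

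**Related text.** Protocol 10.D warns that platelets given during suspensions may dilute the separation and promises: "We will also analyze the impact of suspensions on the platelet count separation". SAP 7.2.2 lists no such analysis. SAP 3.4 separates suspension transfusions only as a supplementary compliance measure. The SAP title page cites protocol v1.3.1 (July 2023); the current protocol is v1.4 (April 2024).

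**The concern.** SAP section 8 states that the study is powered for the Aim 1 outcome and not for the primary safety outcome. The set of observations entering that one test is therefore the definition that most needs to be unambiguous. By the wording of 8.H, a suspension permits transfusion at a higher count than the assigned arm allows, so the disputed observations are the ones most likely to differ from the rest.

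The same choice feeds SE1, whose cut-off of more than 30 equals the planning difference, and the dose difference intended to inform the full trial. The trial is open-label and its statisticians are unblinded (protocol 8.F). A rule left open could be chosen after the by-arm results are visible, or could appear to have been.

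A smaller inconsistency sits alongside. For dose per day, protocol 9.A divides by days on ECMO, whereas protocol Aim 1 and SAP 5.5 use the period from randomization to permanent discontinuation.

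**Working it through.** **The texts side by side**

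| Item | Protocol 9.A / 9.B | Protocol 8.H | SAP |
|---|---|---|---|
| Primary outcome | excluded | not named; included by implication | included (7.2) |
| Platelet dose | excluded | not named; included by implication | included (5.5) |
| Feasibility 1 (SE1) | excluded | included by implication | included (via 7.2.1) |
| Feasibility 6 (SE6) | excluded | excluded | excluded |
| Feasibility 9 (SE9) | excluded | included by implication | no exclusion stated |

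Only endpoint 6 is consistent. Ignoring suspension transfusions and counting them regardless cannot both be followed.

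**The plan's own figure.** Inputs: difference 30, SD 40, effective n 30 per arm (SAP 8), one-sided alpha 0.025 (SAP 7.2.1). The standard error is 40 × √(2/30) = 10.33. Power from the noncentral t with 58 df is 81.5%, which reproduces the stated 81%.

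**Illustration 1: inclusion with no separation within suspensions.** Assumed: separation 30 outside suspensions and 0 within; the same share s of model weight under suspension in each arm; SD 40 and effective n 30 unchanged. The target is d = 30 × (1 − s). The chance that the SE1 estimate exceeds 30 is 1 − Φ((30 − d)/10.33).

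| s | Target d | Power | P(SE1 estimate > 30) |
|---|---|---|---|
| 0 | 30.0 | 81% | 50% |
| 2% | 29.4 | 80% | 48% |
| 5% | 28.5 | 77% | 44% |
| 10% | 27.0 | 73% | 39% |
| 20% | 24.0 | 63% | 28% |

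**Illustration 2: exclusion also costs power.** With compound symmetry and rho 0.3 (SAP 8), a patient with k transfusions contributes k / (1 + 0.3(k − 1)) effective observations: 1.00 for k = 1, 2.105 for k = 4 and 2.273 for k = 5. Assume that each arm has 14 patients with one transfusion, 7 with five, and 4 of 25 with none (16%, within the planned 10% to 20%). Effective n is 14 + 7 × 2.273 = 29.91 from 49 transfusions. Let 5 of the 49 (10%) fall under suspension, with no separation there.

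- (a) They are five patients' only transfusions. Exclusion leaves n = 24.91 (−17%), power 74%. Under inclusion their weight share is 5/29.91 = 0.167, so d = 25.0 and power is 66%.
- (b) They are one each from five of the five-transfusion patients. Exclusion leaves n = 14 + 2 × 2.273 + 5 × 2.105 = 29.07 (−3%), power 80%. Under inclusion the share is 5 × 0.4545/29.91 = 0.076, so d = 27.7 and power is 75%.

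A simulation of 40,000 runs agreed: (a) 65.9% included and 73.9% excluded; (b) 75.2% and 80.5%.

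**Illustration 3: some or all separation kept within suspensions.** With the full 30 kept, inclusion retains 81% power. With 15 kept, d = 30 − 15s. At s = 5%, 10% and 20%, inclusion targets 29.25, 28.5 and 27.0 with power 80%, 77% and 73%. Exclusion, if effective n falls in proportion, gives 79%, 77% and 72%.

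**Illustration 4: unequal shares by arm.** Assumed means are 40 and 70 outside suspensions and 90 within, for both arms.

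- Lower arm 20%, higher arm 5%: (0.95 × 70 + 0.05 × 90) − (0.80 × 40 + 0.20 × 90) = 71 − 50 = 21.0.
- Reversed: (0.80 × 70 + 0.20 × 90) − (0.95 × 40 + 0.05 × 90) = 74 − 42.5 = 31.5.

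**The case against.** The textual conflict is hard to dispute. The serious objections concern what follows from it.

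*Exclusion is not clearly the intended rule.* Protocol 8.H limits exclusion to one secondary endpoint, and the dilution worry in 10.D makes most sense if suspension transfusions are counted. Exclusion also conditions on a post-randomization event that an unblinded clinical team can trigger. These points stand as reasons why the team might choose inclusion. They do not resolve the conflict: 8.H never names the primary outcome, and the section it cites says something different.

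*The power loss may be small.* If half the separation persists within suspensions, the two rules have nearly the same power; in example (a) both give 74%, and in (b) inclusion gives 78% against 80%. Example (a) also puts 5 of 25 patients per arm (20%) under suspension, whereas feasibility criterion 7 aims for under 10%. That criterion leaves out suspensions for decannulation, so the example remains possible. This objection limits any claim about power. The target still moves, to 28.5 at a 10% share.

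*SE1 is one of ten criteria, five are needed, and the rule matters to it only if the two estimates straddle 30.* Correct: the choice can decide SE1 but need not, and SE1 need not decide progression. Dose and SE9 do not bear on the powered test.

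*The version gap may explain the mismatch.* It may, but v1.3.1 is not among the documents, and an explanation does not tell the analyst which rule to apply.

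The closing sentence of 9.B also covers progression to severe bleeding or clotting, and SAP 2.2.5 has no matching exclusion. That parallel mismatch in the safety outcome needs reconciling as well, but it is a separate matter.

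**Conclusion.** The concern holds and must be fixed. The current protocol and the SAP give opposite explicit rules for which transfusions enter the primary analysis and the dose, and the protocol does not agree with itself. This rests on the text alone and on no calculation.

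The numerical consequence cannot be fixed from the documents, because neither gives the share of transfusions under suspension in either arm. Under the stated assumptions the effect of inclusion runs from nothing (full separation kept) to a target of 24 with 63% power (no separation, 20% of weight in each arm). Unequal shares can move the target either way, to 21.0 or 31.5 in the example. Neither rule always has the higher power. The case for settling the rule is that the estimand must be single and pre-specified.

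**What to change.** Before any by-arm analysis of the primary outcome:

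1. Adopt one rule and state it identically in protocol 8.H, 9.A and 9.B and in SAP 7.2, 5.5, SE1 and SE9. Exclusion is the natural default, since 9.A defines the outcome and 9.B repeats the rule; it requires amending SAP 7.2, 5.5 and SE9 and correcting the cross-reference in 8.H. If the team prefers inclusion, amend 9.A and 9.B instead.
2. Name the other rule as a sensitivity analysis in SAP 7.2.2, with the numbers of transfusions and patients under suspension by arm. This also delivers the analysis promised in protocol 10.D.
3. Use one period for dose per day in protocol Aim 1, protocol 9.A and SAP 5.5. If suspension volumes are excluded, say whether suspension hours also leave the denominator; neither document does.
4. Re-issue the SAP against protocol v1.4.

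The cost is a short SAP revision and one or two protocol sentences. No new data are needed, because 8.H provides that "Data monitoring and collection will be unchanged during suspension (including pre-transfusion platelet counts and platelet transfusion volumes") and that suspension length is recorded, so both rules can be run. Under exclusion, somewhat fewer transfusions, and possibly fewer patients, enter the primary model. Protocol 11.B advises against a formal interim analysis of this outcome, so the rule can be settled before its first planned by-arm analysis.
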